Each subject will be randomized to one of 4 treatment sequences in a William's square design (i.e. ABCD, BCDA, CDAB, and DABC).

Treatment Arms and Planned Duration for Individual Subjects:

Screening Period:

All subjects will participate in a screening visit up to 28 days prior to Period 1 study drug dosing.

Treatment Periods:

All subjects will participate in 4 treatment periods. Subjects will be randomized to 1 of 4 treatment sequences. They will be admitted to the clinical research unit (CRU) the day prior to dosing (Day -1) in Period 1, and will be dosed on Day 1 of each treatment period according to their assigned treatment sequence. Subjects will be discharged from the CRU on Day 3 of Period 4, following the collection of all ABP measurements and pharmacokinetic (PK) blood samples. There will be a washout of at least 4 days between each dosing day.

All subjects will be discharged from the study at least 5 days after discharge from Period 4.

Number of Subjects:

Up to 40 subjects may be enrolled to ensure 30 subjects complete the study.

Statistical Analysis:

Cardiovascular parameters that will be assessed by ABPM include peak hourly mean values of SBP, DBP, and MAP, and nadir hourly mean value of PR. The parameters will be listed, and summarized using descriptive statistics, as appropriate. Changes from baseline in cardiovascular parameters SBP, DBP, MAP, and PR will be analyzed to determine the impact of a single dose of sumatriptan 100 mg on the cardiovascular parameters of lasmiditan. A repeated measures linear mixed-effects model with baseline as a covariate, fixed effects for time point, treatment, period (1, 2, 3, or 4), treatment sequence and the treatment by time point interaction, and a random effect for subject will be used. Least squares (LS) means and treatment differences ([lasmiditan + sumatriptan] - [lasmiditan + placebo]) will be calculated and presented with the corresponding confidence intervals (CIs). The same model will be used to assess the impact of a single dose of lasmiditan 200 mg on the cardiovascular parameters of sumatriptan.

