Vital Signs (Supine)	X	X	Predose, 1, 2 and 4 h	24 h			X	Time points may be added for each study period, if warranted and agreed upon between Lilly and the investigator.
ABPM			X	X				The ABPM device will be worn for approximately 2 hours before dosing and will continue to be worn until the 24-hour postdose assessment is complete.
ABPM Training		X						Subjects should be trained on the ABPM device on the evening of Day -1 in Period 1 only. Data from this acclimation period will not be stored or analyzed.
Orthostatic Vital Signs	X							Time points may be added if warranted and agreed upon between Lilly and the investigator.
Clinical Lab Tests	X	X				X	X	See Appendix 2, Clinical Laboratory Tests, for details.

	Screening		Periods 1,	2, 3, and 4		Early Discontinuation	Follow-up	Comments
Procedure prio	-28 to -2 days prior to Day 1/Period 1	Day -1	Day 1	Day 2	Day 3	At least 5 days after discharge from Period 4		
Pregnancy Test	X	X				X	X	Serum pregnancy test will be performed at screening. Urine or serum pregnancy test will be performed at admission to Period 1 and at follow-up.
12-Lead ECG	X		Predose	24 h		X		Single ECGs will be taken.
Physical Exam	X	X		X		X	X	Full medical assessment (including neurological examination) will be performed at screening. After screening, medical assessment only performed to include medical review and targeted examination, as appropriate.
Genetic Sample			Х					Single sample for pharmacogenetic analysis taken prior to dosing on Day 1 of Period 1.
Lasmiditan and Metabolite PK Samples			Predose, 0.5, 1, 1.5, 2, 2.5, 3, 4, 6, 8, 12 h	24 and 36 h	48 h			Sampling times are relative to the time of study treatment administration (0 min).
Sumatriptan PK Samples			Predose, 0.5, 1, 1.5, 2, 2.5, 3, 4, 6, 8, 12 h	24 h				Sampling times are relative to the time of study treatment administration (0 min).

	Screening	Periods 1, 2, 3, and 4			Early Discontinuation	Follow-up	Comments	
Procedure	-28 to -2 days prior to Day 1/Period 1	Day -1	Day 1	Day 2	Day 3		At least 5 days after discharge from Period 4	
Urine Sample for CrCl			0-6, 6-12, and 12-18 h	18-24, 24-30 and 30-36 h	36-42 and 42-48 h			Urine collection for the determination of CrCl.
Renal Biomarker Samples			Predose, 0.5, 1, 1.5, 2, 2.5, 3, 4, 6, 8, 12 h	24 and 36 h	48 h			Sampling times are relative to the time of study treatment administration (0 min).

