5.1. Overall Design

This is a randomized, double-blind, crossover study with 4 study periods in healthy subjects. All subjects will participate in 4 treatment periods. The treatments are as follows:

- Treatment A: lasmiditan 200 mg + sumatriptan 100 mg
- Treatment B: lasmiditan 200 mg + placebo
- Treatment C: sumatriptan 100 mg + placebo
- Treatment D: placebo + placebo

Each subject will be randomized to one of 4 treatment sequences in a William's square design as outlined in Table LAHU.2.

Table LAHU.2. Sequences in Study LAHU

Sequence	Period 1	Period 2	Period 3	Period 4
1	Lasmiditan + sumatriptan	Lasmiditan + placebo	Sumatriptan + placebo	Placebo + placebo
2	Lasmiditan + placebo	Sumatriptan + placebo	Placebo + placebo	Lasmiditan + sumatriptan
3	Sumatriptan + placebo	Placebo + placebo	Lasmiditan + sumatriptan	Lasmiditan + placebo
4	Placebo + placebo	Lasmiditan + sumatriptan	Lasmiditan + placebo	Sumatriptan + placebo

Screening Period:

All subjects will participate in a screening visit up to 28 days prior to Period 1 study drug dosing.

Treatment Periods:

All subjects will participate in 4 treatment periods. Subjects will be randomized to one of 4 treatment sequences. They will be admitted to the clinical research unit (CRU) the day prior to dosing (Day -1) in Period 1, and will be dosed on Day 1 of each treatment period according to their assigned treatment sequence (Table LAHU.2). Subjects will be discharged from the CRU on Day 3 of Period 4 following the collection of all ABP measurements and PK blood samples. There will be a washout of at least 4 days between each dosing day.

All subjects will be discharged from the study at least 5 days after discharge from Period 4.

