5.4. Scientific Rationale for Study Design

A double-blind (subject- and investigator-blinded), randomized, and placebo-controlled design is being used to minimize bias on the primary objective of this study.

The study blind will be maintained by either use of a blindfold, or placement of the tablets in an amber vial to disguise their appearance; the sumatriptan tablets to be used in this study will be similar in shape and size to both lasmiditan and lasmiditan placebo (round and approximately 10 mm in diameter), therefore lasmiditan placebo will also be used as the placebo for sumatriptan.

A crossover design improves the sensitivity for detecting any cardiovascular signals by means of vital signs (as are described in Section 3.2). Conducting the study in healthy subjects mitigates the potential confounding effects of the disease state and concomitant medications.

The washout period is at least 4 days, which is adequate based on the half-life of lasmiditan.

The nonclinical and clinical data enable conducting clinical pharmacology studies in healthy subjects. The single dose design of this study limits exposure of subjects to lasmiditan and is appropriate to address the study objectives.

Preliminary data suggest that lasmiditan may inhibit renal transporters involved in the active secretion of creatinine into the urine, which can lead to a decrease in the renal clearance of creatinine in vivo and subsequent increase in serum creatinine. The change in creatinine renal clearance is often delayed and transient. Hence, frequent sampling with urine collection is necessary for capturing temporal changes in creatinine disposition. The inclusion of serum cystatin C, which provides a more precise measure of glomerular filtration rate (GFR), enables differentiation between changes in creatinine transport versus change in renal function.

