7.2. Method of Treatment Assignment

All subjects will participate in 4 treatment periods. The treatments are as follows:

- Treatment A: lasmiditan 200 mg + sumatriptan 100 mg
- Treatment B: lasmiditan 200 mg + placebo
- Treatment C: sumatriptan 100 mg + placebo
- Treatment D: placebo + placebo

Each subject will be randomized to one of 4 treatment sequences in a William's square design (i.e., ABCD, BCDA, CDAB, and DABC) using a computer-generated allocation schedule.

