10.3.3.2. Statistical Inference of Cardiovascular Parameters

Cardiovascular parameters will be listed, and summarized using descriptive statistics, as appropriate.

Baseline value will be defined as the mean value during the 2 hours pre-dose for each period. Changes from baseline in cardiovascular parameters SBP, DBP, MAP, and PR will be analyzed to determine the impact of a single dose of sumatriptan 100 mg on the cardiovascular parameters

of lasmiditan. A repeated measures linear mixed-effects model with baseline as a covariate, fixed effects for time point, treatment, period (1, 2, 3, or 4), treatment sequence, and the treatment by time point interaction, and a random effect for subject will be used. Least squares (LS) means and treatment differences ([lasmiditan + sumatriptan] - [lasmiditan + placebo]) will be calculated and presented with the corresponding CIs. The same model will be used to assess the impact of a single dose of lasmiditan 200 mg on the cardiovascular parameters of sumatriptan.

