5. STUDY DESIGN

This is a randomized, double-blind, crossover study with 4 study periods in healthy subjects. All subjects will participate in 4 treatment periods. The treatments are as follows:

- Treatment A: lasmiditan 200 mg + sumatriptan 100 mg
- Treatment B: lasmiditan 200 mg + placebo
- Treatment C: sumatriptan 100 mg + placebo
- Treatment D: placebo + placebo

Each subject will be randomized to one of 4 treatment sequences in a William's square design as outlined in Table 1.

Table 1. Sequences in Study LAHU

Sequence	Period 1	Period 2	Period 3	Period 4
1	Lasmiditan + sumatriptan	Lasmiditan + placebo	Sumatriptan + placebo	Placebo + placebo
2	Lasmiditan + placebo	Sumatriptan + placebo	Placebo + placebo	Lasmiditan + sumatriptan
3	Sumatriptan + placebo	Placebo + placebo	Lasmiditan + sumatriptan	Lasmiditan + placebo
4	Placebo + placebo	Lasmiditan + sumatriptan	Lasmiditan + placebo	Sumatriptan + placebo

Screening Period:

All subjects will participate in a screening visit up to 28 days prior to Period 1 study drug dosing.

Treatment Periods:

All subjects will participate in 4 treatment periods. Subjects will be randomized to one of 4 treatment sequences. They will be admitted to the clinical research unit (CRU) the day prior to dosing (Day -1) in Period 1, and will be dosed on Day 1 of each treatment period according to their assigned treatment sequence (Table 1). Subjects will be discharged from the CRU on Day 3 of Period 4 following the collection of all ambulatory blood pressure (ABP) measurements and PK blood samples.

There will be a washout of at least 4 days between each dosing day.

All subjects will be discharged from the study at least 5 days after discharge from Period 4.

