9.4.2 Cardiovascular Statistical Methodology

Primary analysis

Changes from baseline in peak hourly mean values of cardiovascular parameters SBP, DBP, and MAP, and nadir hourly mean values of PR will be analysed to determine the impact of a single dose of sumatriptan 100 mg on the peak/nadir hourly mean values of the cardiovascular parameters of lasmiditan. A linear mixed-effects model with baseline as a covariate, fixed effects for treatment, period (1, 2, 3, or 4), and treatment sequence, and a random effect for subject will be used. Least squares (LS) means and treatment differences ($[\text{lasmiditan} + \text{sumatriptan}] - [\text{lasmiditan} + \text{placebo}]$) will be calculated and presented with the corresponding CIs.

Primary cardiovascular parameters may be log-transformed prior to the statistical analysis if a review of the data indicates that the assumption of normality is violated.

The same model will be used to assess the impact of a single dose of lasmiditan 200 mg on the peak/nadir hourly mean values of the cardiovascular parameters of sumatriptan.

An example of the SAS code that will be used is as follows:

```
proc mixed data=xxx;  
  class trtmnt period seq subject;  
  model primcard = base trtmnt period seq / alpha=0.1 cl ddfm=kr;  
  random subject;  
  lsmeans trtmnt / alpha=0.1 cl pdiff;  
run;
```

where 'primcard' is the change from baseline in the peak/nadir hourly mean values of the primary cardiovascular parameters SBP, DBP, MAP/PR respectively.

Repeated measures analysis:

Changes from baseline in cardiovascular parameters will be evaluated to determine the impact of a single oral dose of sumatriptan 100 mg on the cardiovascular parameters of single oral dose of lasmiditan 200 mg.

A repeated measures linear mixed-effects model with baseline as a covariate, fixed effects for time point, treatment, period (1, 2, 3, or 4), treatment sequence, and the treatment by time point interaction, and a random effect for subject will be used. LS means and treatment differences ([lasmiditan + sumatriptan] – [lasmiditan + placebo]) will be calculated and presented with the corresponding 90% CIs.

An example of the SAS code that will be used is as follows:

```
proc mixed data=xxx;  
  class trtmnt subject time period seq;  
  model cardio = base time trtmnt period seq trtmnt*time / alpha=0.1 cl ddfm=kr;  
  repeated time / type=un subject=subject;  
  random subject;  
  lsmeans trtmnt*time / alpha=0.1 cl pdiff;  
run;
```

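### The sequences labelled a William's square form a cyclic Latin square, so first-order carry-over is not balanced in the primary A−B and A−C contrasts

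*Protocol*

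**What the plan says.** The synopsis and section 7.2 of the protocol both name a William's square and list the sequences; section 7.2 has "square design (i.e., ABCD, BCDA, CDAB, and DABC) using a computer-generated allocation schedule" and the synopsis has "square design (i.e. ABCD, BCDA, CDAB, and DABC". Protocol section 5.1 refers to a William's "square design as outlined in Table LAHU.2" and SAP section 5 to a William's "square design as outlined in Table 1". Both tables write out the same four rows treatment by treatment, so this is not a typing slip in one place.

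The primary cardiovascular contrast is A−B, the combination minus lasmiditan alone. A−C is not written as a formula, but it follows from using the same model for the effect of lasmiditan on sumatriptan. SAP section 9.4.2 gives the primary model as "A linear mixed-effects model with baseline as a covariate, fixed effects for treatment, period (1, 2, 3, or 4), and treatment sequence", with a random subject effect. Neither that model nor the repeated-measures model in protocol section 10.3.3.2 and SAP section 9.4.2 has a carry-over term. The baseline is specific to each period: "Baseline value will be defined as the mean value during the 2 hours pre-dose for each period".

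Carry-over is left to the washout. Protocol section 5.4 says: "The washout period is at least 4 days, which is adequate based on the half-life of lasmiditan". Section 3.2 gives that half-life as about 4 to 6 hours.

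**The concern.** What defines a Williams square is that every treatment is immediately preceded by every other treatment equally often. A reader told that this design was used will assume that protection is in place.

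In the listed sequences each treatment has only one possible predecessor. From period 2 on, A is measured only after D, B only after A, C only after B and D only after C. If the combination left blood pressure slightly raised into the next period, the whole of that residual would fall on lasmiditan alone and none on the combination. A−B would shrink, so the study would lean towards missing an added pressor effect, which is the effect it is meant to measure.

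Additive period effects, and carry-over that is equal for all treatments, still cancel. Only differential carry-over is at issue.

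**Working it through.** **Inputs.** Sequences: protocol section 7.2 and Table LAHU.2. SD of the within-subject SBP change 12.7 mmHg, 30 completers and half-width 4.6 mmHg: protocol section 10.1. Washout of at least 4 days (96 h): sections 5.1 and 5.4. Half-life 4 to 6 h: section 3.2. Equal allocation and complete data are assumed.

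**1. The plan's own precision figure.** Half-width not exceeded with 90% probability = t(0.95, 29) × 12.7/√30 × √(χ²(0.90, 29)/29) = 4.57 mmHg. The stated 4.6 mmHg reproduces. It does not depend on which square is used, because the A−B variance without carry-over terms is the same in both.

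**2. Count of adjacent ordered pairs.**

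| Square | Pairs that occur |
|---|---|
| ABCD, BCDA, CDAB, DABC (listed) | AB, BC, CD, DA three times each; the other 8 never |
| ABDC, BCAD, CDBA, DACB (Williams) | all 12 once each |

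**3. Bias when carry-over is not modelled.** Every subject receives every treatment, and every treatment appears once in each period. Treatment contrasts adjusted for subject and period are therefore plain differences of treatment means. Write c_X for the carry-over left by treatment X. In the listed square the mean of A contains 0.75 c_D, that of B 0.75 c_A and that of C 0.75 c_B. In the Williams square each mean contains 0.25 times the sum of the other three. Hence:

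| Contrast | Listed square | Williams square |
|---|---|---|
| A−B | 0.75 (c_D − c_A) | 0.25 (c_B − c_A) |
| A−C | 0.75 (c_D − c_B) | 0.25 (c_C − c_A) |

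The two columns weight different differentials. The listed square sets an active residual against placebo; the Williams square sets one active residual against another.

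**4. Allowing for the baseline covariate.** With slope b of the postdose value on baseline, the weight applies to (postdose residual − b × predose residual). The documents do not give b, so take 0 to 0.9. Assume that A leaves 2 mmHg, present equally before and after dosing, and that the other treatments leave none. The A−B bias size is then 0.75 × 2 × (1 − b) in the listed square and 0.25 × 2 × (1 − b) in the Williams square:

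| b | Listed (mmHg) | Williams (mmHg) |
|---|---|---|
| 0 | 1.5 | 0.5 |
| 0.3 | 1.05 | 0.35 |
| 0.6 | 0.60 | 0.20 |
| 0.9 | 0.15 | 0.05 |

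A residual that shows only after dosing gives 1.5 against 0.5 mmHg at any b.

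The SAP's primary model (random subject, sequence, baseline) was also simulated for the listed square with 10,000 subjects, within-subject SD 12.7/√2 = 9.0 and an assumed between-subject SD of 10. At within-subject correlations of 0, 0.3, 0.6 and 0.9, the bias for the persistent residual was 0.97, 0.64, 0.24 and 0.10 mmHg (simulation SE 0.06 to 0.13). These values are lower than in the table because stable differences between subjects raise b. The postdose-only residual gave 1.38 to 1.49 mmHg.

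**5. Differential needed to move A−B by the planned half-width, without baseline.** Listed: 4.6/0.75 = 6.1 mmHg between D and A. Williams: 4.6/0.25 = 18.4 mmHg between B and A.

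**6. Cost of modelling carry-over later.** Adding carry-over terms multiplies the contrast variance by 5.5 in the listed square and 1.10 in the Williams square. The half-width becomes 4.57 × √5.5 = 10.7 mmHg or 4.57 × √1.10 = 4.8 mmHg.

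**7. Washout.** 96/6 = 16 to 96/4 = 24 half-lives. The remaining fraction of lasmiditan is about 1.5 × 10⁻⁵ to 6 × 10⁻⁸.

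**The case against.** The strongest reply is that there is little to carry over. Lasmiditan is essentially gone after 96 hours, and any sumatriptan half-life up to 96/5 = 19.2 h would still allow five half-lives. Protocol section 3.2 calls lasmiditan's vital-sign effects transient, and sections 3.1 and 3.3 say the same of sumatriptan's pressor effect. A 2 mmHg residual four days after one dose has no support in the text, and no mechanism is offered for one that appears only after dosing. Leaving out a carry-over term is ordinary practice when washout is relied on, and a Latin square balanced for period is then valid. All of this stands as an argument about size. It does not make the label right. The washout argument also covers lasmiditan only: no half-life is given for sumatriptan or the metabolites, and nothing is said about how long the blood pressure effect itself lasts.

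A second reply is that the 2 mmHg example is one-sided. Without baseline, a residual from A alone biases A−C by 0 in the listed square and by 0.25 × 2 = 0.5 mmHg in the Williams square, so the replacement is slightly worse there. This is correct. If the residual comes from lasmiditan (A and B each 2 mmHg), the listed square gives 1.5 mmHg in both contrasts and the Williams square gives 0 in A−B and 0.5 in A−C. A Williams square reduces the weights; it does not remove unmodelled carry-over.

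A third reply is that the checks already exist. Each period has a predose sample under "Lasmiditan and Metabolite PK Samples" in the Schedule of Activities, predose sumatriptan samples and its own ABPM baseline. That is true, but no planned output arranges these by preceding treatment, and SAP section 9.3.1 sets the average predose concentration to zero in the mean profiles.

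**Conclusion.** The concern holds. The design named in the protocol and SAP is not the design listed: the sequences are a cyclic Latin square, with 4 of 12 ordered pairs, and first-order carry-over is not balanced in A−B or A−C. This is a matter of counting and rests on no assumption. The weight of 0.75 assumes equal allocation, complete data and no help from baseline.

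The likely numerical effect is small. On an assumed 2 mmHg residual from the combination it is 0.15 to 1.5 mmHg in A−B by the formula, and 0.10 to 0.97 mmHg in the simulated SAP model if the residual is already present before dosing. On the documents' own half-life even 2 mmHg looks generous. The point does not threaten the study's validity. It should be fixed because the plan claims a safeguard it does not have, because later adjustment for carry-over would more than double the interval width, and because real balance is nearly free before dosing.

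**What to change.** **Before first dosing:** replace the sequences in the protocol synopsis, Table LAHU.2, section 7.2 and SAP Table 1 with a true Williams square, for example ABDC, BCAD, CDBA, DACB, and regenerate the allocation schedule. The cost is one protocol amendment, a matching SAP edit and a new schedule. The numbers of subjects, periods and sequences, the model terms and the 4.6 mmHg precision target all stay as they are. SAP section 3 requires sign-off before the first administration, so the correction can be made at that point.

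**If dosing has begun** (the documents do not show whether it has): keep the schedule and change the label to cyclic Latin square in all four places. State that first-order carry-over is not balanced and that the analysis relies on washout of both drugs. Add one descriptive table of predose concentrations (lasmiditan, metabolites, sumatriptan) and predose ABPM baseline by preceding treatment. This costs a wording change and one table from data already collected.

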7.2.1. Timing of Doses

The doses will be administered at approximately the same time on Day 1 of each treatment period. The actual time of all dose administrations will be recorded in the subject's electronic case report form (eCRF).

7.3. Blinding

Each subject will either be blindfolded at each dosing occasion, or will receive the study drug in an amber vial, to maintain the study blind. Blinding will also be maintained throughout the conduct of the study as described in the separate Blinding Plan.

Emergency codes will be available to the investigator. A code, which reveals the treatment sequence for a specific study subject, may be opened during the study only if the subject's well-being requires knowledge of the subject's treatment assignment.

If a subject's study treatment assignment is unblinded, the subject must be discontinued from the study, unless the investigator obtains specific approval from a Lilly clinical pharmacologist or clinical research physician (CRP) for the study participant to continue in the study. During the study, emergency unblinding should occur only by accessing the study subject's emergency code.

In case of an emergency, the investigator has the sole responsibility for determining if unblinding of a subject's treatment assignment is warranted for medical management of the event. The subject's safety must always be the first consideration in making such a determination. If the investigator decides that unblinding is warranted, it is the responsibility of the investigator to promptly document the decision and rationale and notify Lilly as soon as possible.

Upon completion of the study, all codes must be returned to Lilly or its designee.

